The interventionist will have a teaching plan with guidelines on time use for TRUST topics. Each session will include a trust-building topic and a depression management topic, a discussion portion and a practice portion. With the trust building portion, we will focus on honesty, reliability, and emotional connection. For example, the Honesty portion will teach adolescent and parent to share personal details about themselves without judging one another. Parents often get upset when their adolescent shares personal details with them and then jump to conclusions, judgment, and reprimands, which breaks down trust. The intervention will discuss this, then have adolescent-parent dyads practice sharing small truths and being receptive to those disclosures. With the Reliability portion, we'll discuss that reliability means following through on your word. Dyads will make small promises to one another, then try to follow through on keeping the promises in the week between sessions. Emotional Connection is built when each person is receptive to disclosures and keeps promises.

With the depression self-management portion, we will focus on stress management, sleep, medication adherence, and appointment keeping only. We will discuss why these topics are important to health and identify ways to improve them. Each adolescent-parent dyad will set goals to improve in each of these areas, then

identify a way to do that. For example, with stress management it could be taking a walk to de-stress, with sleep it might be giving up screen time one hour before bed. Making goals and keeping them is also a form of making promises and keeping them--thus connecting and reinforcing the concepts of trust and a healthy lifestyle.

We will conduct fidelity monitoring of the intervention groups. Each session of the TRUST intervention will be audio-recorded. Half of the sessions will be randomly selected for review using an investigator-developed fidelity checklist composed of the key elements of the intervention ²⁶. Fidelity will be assessed by checking that each of the assigned topics from the teaching plan are discussed during the appropriate meetings.

This is a social/behavioral research study. No drugs or devices will be tested as interventions with the research participants. No source records, such as medical or educational records, will be used to collect data about participants.

(4) Study Procedures and Time Requirement:

Study Procedures	Estimated time requirement	
	Group 1	Group 2
Prescreening	5 minutes	5 minutes
Screening	30 minutes	30 minutes
Study Visit 1 (Baseline)	30 minutes	30 minutes
Intervention week 1	45 minutes	1 hours
Intervention week 2	45 minutes	1 hours
Intervention week 3	45 minutes	1 hours
Intervention week 4	45 minutes	1 hours
Intervention week 5	45 minutes	1 hours
Intervention week 6	45 minutes	1 hours
Intervention week 7	45 minutes	1 hours
Intervention week 8	45 minutes	1 hours
Study Visit 2 (3 months)	30 minutes	30 minutes
Study Visit 3 (6 months)	30 minutes	30 minutes
Total	8 hours 5 minutes	10 hours 35 minutes

ClinicalTrials.gov Information

Has this study been registered on ClinicalTrials.gov?

Yes. Provide the following:

- i. The ClinicalTrials.gov identifier: 00220503
- ii. Investigator/sponsor responsible for registering: [name]

No. Explain if there are plans to register or why registration is not required.

List of Data to be Collected

1. Indicate what identifiers you will collect

- Name
- Address
- Dates related to an individual (*birthdate*)
- Telephone number
- Fax number
- Email address

- Social security number
- Medical record number
- Health plan beneficiary number
- Account number
- Certificate/license number
- Any vehicle or other device serial
- Device identifiers or serial numbers
- Web URL
- Internet protocol (IP) address
- Finger or voice prints
- Photographic (video) images
- Other: Any characteristic that would uniquely identify the individual

Data Analysis Plan

(1) Statistical Analyses. Each participant will be assigned a unique identifier for tracking purposes and all raw data will be uploaded to the secure database in REDCap. We will explore all variables using descriptive statistics. To address the Aims 1-2, we will use a linear mixed effects model. To address Aim 3, we will apply usual mediation techniques.

Confidentiality of Specimens and Banking

Salivary specimens and cheek swabs are canceled due to Covid-19. Specimens collected prior to Covid-19 were handled as follows. Salivary specimens and cheek swabs will be collected and banked until full processing can occur. The specimens will be stored in the Frances Payne Bolton School of Nursing biomarker laboratory. Specimen testing is funded with internal monies; therefore, specimens will not be transferred to other researchers at this time.

Saliva specimens will be obtained from each adolescent at baseline and 3-month data collections. The saliva samples will be collected by study personnel and labeled with the participant's alpha-numeric study identification code. Fifteen minutes pre/post the dyadic behavioral interaction assessment, measures of salivary oxytocin levels of adolescents will be collected using SalivaBio passive drool salivary collection kits (Salimetrics LLC, State College, PA). Salivary samples will immediately be placed on ice, transported to the laboratory by study personnel, and transferred to a locked -80°C freezer until processed and analyzed. Time from collection to freezing will be less than 1 hour. Salivary specimens will be processed per standard operating protocols to minimize non-biological technical bias. Salivary specimens will be stored for approximately 1 year, until enough samples have been collected to fill a single assay plate. Only study personnel will have access to the specimens. The remainder of the specimens will be destroyed after analysis. The salivary oxytocin testing is funded with internal funding and will not be transferred to other researchers.

Cheek swabs obtained by a Registered Nurse research assistant will be collected only a single time during the study and will be used for OXTR genotyping. The Registered Nurse research assistant will obtain the cheek swabs, label them with the participant's alpha-numeric study identification code, transport them to the lab at the Case Western Reserve University Frances Payne Bolton School of Nursing, and preserve them in lysis buffer until DNA extraction. OXTR rs53576 will be genotyped using the TaqMan genotyping platform. The TaqMan Genotyping Assay and TaqMan Genotyping Master Mix will be ordered from Thermo Fisher Scientific (Thermo Fisher Scientific, Waltham, MA, <https://www.fishersci.com>). Genotyping will be performed in a 20- μ l system containing 10 μ l of TaqMan Genotyping Master Mix, 1 μ l of

TaqMan Genotyping Assay, and 1 μ l genomic DNA using the StepOne Plus real-time PCR system (Applied Biosystems, Foster City, CA). Allele determination will be performed using StepOne Plus software v2.3 (Applied Biosystems). Cheek swab specimens will be stored for up to 10 years and may be used for other genetic analyses. The remainder of the specimens will be destroyed after 10 years or when they are no longer viable. Only study personnel will have access to the specimens. The OXTR genotyping is funded with internal funding and will not be transferred to other researchers. Cheek swabs will be labeled only with study id and date; no master list will be made of identities and no attempt will be made to re-identify the specimens.

Are you storing the specimen for future use for other research projects?

Yes
 No

Confidentiality of Data

(1) To maintain the confidentiality of the data, I will use a unique study identifier (not derived from the participants' personal identifiers) to code individuals' data and I will store this ID log separate from study data.

(2) How are you storing your electronic data?

UH Redcap
 CWRU Redcap
 Secure Research Environment (SRE)
 CWRU Box
 OnCore
 UH Secure Network Drive (S:)
 CWRU Secure Network Drive
 Other: List storage method and provide justification

(3) I acknowledge that paper research data and documents will be stored in a double-locked secure environment in the following location:

Location: Locked file cabinet in PI [name]'s locked research office located in the School of Nursing

(4) Data Sharing: N/A

HIPAA Authorization

If you are going to be accessing PHI (Protected Health Information), indicate how HIPAA authorization will be obtained (check all that apply):

HIPAA authorization is in the consent form
 Requesting a full or partial waiver of HIPAA for prescreening
 Requesting a full or partial waiver of HIPAA

(1) We are not collecting data from a covered entity; therefore, HIPAA authorization is not necessary.

(2) Research records will be kept in a locked file and access will be limited to the researchers. In addition, research guidelines require that we provide access to regulatory bodies such as the

University IRB, regulatory agencies, and the Center for Reducing on Health Disparities at MetroHealth to evaluate the safety of this project.

(3) Personal identifiers will be kept for 6 years after giving study consent, which is approximately 5 years after the study ends and data analysis begins.

Risks to Research Participants

(1) The level of risk from the proposed trial is no more than encountered in daily life and is minimal relative to other clinical trials that test drugs, devices, or medical procedures. Of note, we will not be completing the behavioral interaction, RSA, salivary samples, or cheek swabs portions of the study while restrictions associated with the COVID-19 pandemic are in-place. We will resume this part of our study when public health recommendations allow for this in-person data collection. There is a small risk of loss of confidentiality by participating in this study. Our team takes participant confidentiality serious and implements several safeguards against loss of confidentiality. However, it is possible that being seen on campus with members of our team will identify participants' role in the Level Up Study to passersby.

The risks associated with gathering information from participants by properly trained and supervised research assistants are low. Participants may experience discomfort by some questions assessing stress and depression. In prior research, we have used these measures or similar measures with this adolescent-parent dyad population and found that adolescent-parent dyads were comfortable with the interviews. However, all participants will be instructed that they can stop the interview at any time or can choose to skip any question that they wish. Our investigators and staff are experienced interviewers in research involving adolescent-parent dyads, and we have rarely encountered participant reactions more adverse than transient awkwardness, embarrassment, or mild discomfort. We are prepared to deal with such events and have a protocol that instructs the data collector how to obtain assistance for psychological issues should they arise.

There is the potential for stigmatization due to depression diagnosis; however, measurements are taken in private and all results are reported privately in a sensitive and culturally appropriate manner. The nature of this study includes adolescents with a diagnosis of depression. If the adolescent becomes upset during study procedures, a study research assistant and the participant's parent will be available to support and comfort the adolescent participant if needed. If questionnaires indicate symptoms suggestive of severe depression or suicidal ideation, the results will be reviewed with [name], Ph.D. (co-investigator, licensed clinical psychologist, #6732) who will consult with the participant to determine whether the participant is in need of a referral for further evaluation and treatment.

(2) Although this study is deemed as having minimal risk, we recognize there are some unanticipated risks. An example on an unanticipated risk is that participants may be disappointed with the intervention group to which they are assigned.

(3) As a social/behavioral intervention study, no procedure in this study is a risk to an embryo or fetus should the research participant may or may become pregnant.

(4) There are no known risks to others who are not research participants.

(5) Drs. [name] and [name] have conducted previous research protocols that involve adolescent-parent dyads and have experienced research assistants and established protocols for quality assurance, crisis intervention and referral, as well as initial and ongoing staff training. The research assistants hired for this project will have prior experience working with adolescent-parent dyads. If questionnaires indicate symptoms suggestive of severe depression or suicidal ideation, the results will be reviewed with [name], Ph.D. (co-investigator, licensed clinical psychologist, #6732) who will consult with the youth and/or parent/guardian to determine whether the youth or parent/guardian is in need of a referral for further evaluation and treatment.

Provisions to Protect the Privacy Interests of Research Participants

To protect participants' privacy, several measures will be taken. During COVID-19 data collection, adolescents and parents will be encouraged to complete the surveys in private spaces. Following the easing of restrictions associated with the COVID-19 pandemic, in-person data collection will resume and the following precautions will be taken. All study procedures will be carried out in private rooms. As participants are completing questionnaires, study staff will remain available for questions, but avoid moving around the room in any way that would allow the staff to see the participants' questionnaire responses. Both parents and adolescents will receive separate tablet computers to complete the questionnaires simultaneously, so that participants are each engaged with their own questionnaires and promote privacy of the other participant. If participants are uncomfortable with the tablet computer, we will make arrangements to complete the questionnaires by participant's choice of interview by study staff or by paper and pencil. During the cheek swab, participants will be allowed to swab their own mouths with direction from study staff, if the participants' desire. When placing the heart rate monitoring leads on participants' chests for the respiratory sinus arrhythmia testing, this will be done in a private room and by same gendered study staff, if desired by participants. During the behavioral interaction assessment, study staff will remain nearby but step out of the room, in order to help adolescent and parent participants' feel comfortable during the discussion.

Paper and pencil questionnaire completion will be a rare event. In the event of participant's choice or internet connectivity problems, survey data will be collected through paper and pencil surveys. Research staff will be responsible for entering survey data directly into REDCap once internet connectivity has become a non-issue. Paper and pencil surveys will be stored in a locked, filing cabinet in PI [name]'s locked research office. Only key research staff will have access to this office and access to the key to the filing cabinet.

Potential Benefit to Research Participants

Participants participating in this research may learn new skills for better managing their stress and sleep quality; medication adherence and appointment keeping skills may improve their health; and trust-building exercises may improve the quality of the adolescent-parent relationship. These improvements may be short-term or long-term changes. We anticipate that our findings will demonstrate the linkages between a trust-building behavior change strategy and health behavior change that will help adolescents and parents improve their health.

Withdrawal of Research Participants

Research participants will be withdrawn from the intervention without their consent under these circumstances:

1. participants display disruptive behavior during the group intervention sessions,
2. evidence of abuse between parent and adolescent dyad, or
3. indication that a participant may be a harm to themselves or others.

In the event that participants are removed from the intervention, PI [name] will notify participants of their removal. Participant dyads will receive a closeout packet, which will contain a list of community resources for further depression symptom management treatment. Participants will also receive study personnel contact information to follow up on study outcomes. At this time, we will also update participants' contact information and ask if they are willing to be contacted for further study visits, if appropriate.

Alternatives to Participation

HRP-503BIO	Biomedical Protocol	
Approved:	1/23/2018	Prior Version:

- (1) No one will be required to participate in our study. Other available clinical treats are individual, family, or group therapy. Community self-management treatments available include stress management classes, such as yoga.
- (2) Standard of care therapy, including depression medication and counseling, should be continued regardless of participation. Self-management treatments are considered adjuvant to clinical treatment. We anticipate and encourage our participants to continue standard of care therapy.
- (3) Since self-management training is adjuvant to standard of care treatment, another option is to not participate.

Costs to Research Participants

- (1) There are no costs to participation in this study. Our study compensates participants for their time and travel costs.
- (2) Participants' health insurance will not be charged for any services provided in this study.
- (3) This study will pay for the costs of transportation to study visits; cost of group intervention sessions including healthy snacks and small gifts; time to complete study visits; costs of surveys; and costs of respiratory sinus arrhythmia/behavioral interaction testing.

Research Participant Compensation

Participation in the study requires time and effort. Because of this, compensation for time spent completing the study surveys, respiratory sinus arrhythmia (RSA), and behavioral interaction assessment will be provided. Each adolescent and parent participant will receive a \$25 gift card for completing each structured interview and each behavioral interaction assessment with RSA. Thus, adolescent-parent dyad participants who complete all interviews (\$150 total) and undergo two behavioral interactions with RSA (\$100 total) may receive a total up to \$250. This amount is consistent with our previous work and is not perceived to be coercive by members of the community advisory board.

During the intervention groups, participants may receive small gifts (each valued at less than \$15) intended to assist them in meeting intervention goals. Participants may receive small gifts such as an eye mask to promote sleep, a 7-day medication box to promote medication adherence, a book about parent/teen communication, and a yoga mat. Healthy snacks will be made available to participants during the group sessions. A schedule of compensation is listed below.

Compensation		
Study Procedures	Adolescent	Parent
Study Visit 1 (Baseline) Questionnaires RSA/behavioral interaction	Transportation (paused) \$25 gift card \$25 gift card (paused)	Transportation (paused) \$25 gift card \$25 gift card (paused)
Intervention week 1	Small gifts	Small gifts
Intervention week 2	Small gifts	Small gifts
Intervention week 3	Small gifts	Small gifts
Intervention week 4	Small gifts	Small gifts
Intervention week 5	Small gifts	Small gifts
Intervention week 6	Small gifts	Small gifts
Intervention week 7	Small gifts	Small gifts
Intervention week 8	Small gifts	Small gifts
Study Visit 2 (3 months) Questionnaires RSA/behavioral interaction	Transportation (paused) \$25 gift card \$25 gift card (paused)	Transportation (paused) \$25 gift card \$25 gift card (paused)
Study Visit 3 (6 months) Questionnaires	Transportation (paused) \$25 gift card	Transportation (paused) \$25 gift card
Total	\$75 gift cards + small gifts; transportation + snacks (paused)	\$75 gift cards + small gifts; transportation + snacks (paused)

Compensation for Research Related Injury

Describe who will pay for the costs of medical treatment and/or compensation in the event of a research related injury:

- Funding agency is providing some/all payment for injury
- Funding agency is providing no payment for injury
- Not applicable

Provisions to Monitor the Data to Ensure the Safety of Research Participants

(1) The data and safety monitoring plan for this study includes an official committee. The committee members who are outside the study team will review data on the study as provided by Drs. [name] and [name] and conduct random auditing of the research records to assess study safety and regulatory compliance. Twice annually throughout the project, this committee will review data on this study regarding 1) study safety, including auditing selected cases for compliance with IRB requirements, conformance with informed consent requirements, verification of source documents, and investigator compliance; 2) minimizing research-associated risk; and 3) protecting the confidentiality of participant data. In addition, it will review all causes of mortality and issues with participation. The rate of recruitment refusal (percent and reasons) and participant attrition (percent and reasons) will be tracked and reported at these reviews. Differential attrition from the intervention arms also will be monitored. If concerns or problems are identified by the Data and Safety Monitoring Committee (DSMC), they will be reported to the IRB and the sponsor via email by [name] and [name], respectively, within 3 business days after they are identified. If there are recommendations made by the DSMC, the action plan for response or notice of any actions taken by the IRB regarding the research and any responses to those actions will be provided to sponsor officials within 2 weeks.

At the onset and across the duration of the study, all staff and Investigators will have instructional review of the nature and types of unanticipated and adverse events as described

by the sponsor and the CWRU IRB. As they occur, all unanticipated events and adverse events will immediately be reported to the PI who will report them to the IRB according to the IRB protocol reporting procedures for both serious and non-serious adverse event and unanticipated problem reporting. These will be summarized in the twice annual reports to the DSMC. Annual progress reports to the IRB and the sponsor will include a summary of the DSMC's activities and findings as well as any adverse events regarding human participants. Program Officials of the sponsor will be informed in a timely manner (3 business days) of unanticipated problems (e.g., a data breach) or unexpected serious adverse events that may be related to the study protocol or IRB-approved revisions to the study protocol that indicate a change in risk for participants.

(2) A Data and Safety Monitoring Committee (DSMC) will be established for this study. This DSMC will independent of the study sponsor and will meet every 6 months of the study. [name] will chair the committee and be responsible to submit reports to the study sponsor and IRB within 2 weeks of the meeting. DSMC members include:

[name], an experienced family researcher ([contact])
 [name], an NIH-funded researcher with parent/child dyads ([contact])
 [name], a statistician not involved with the project ([contact])
 [name], neuroscience of health behavior researcher ([contact])
 [name], PI ([contact])
 [name], Co-I ([contact])

Community-Based Participatory Research: N/A

Non-Local Recruitment Methods for Multi-Site Studies: N/A

Multi-Site Research Communication Plan: N/A

Drugs or Devices: N/A

3. Avenevoli S, Swendsen J, He J, Burstein M, Merikangas K. Major depression in the National Comorbidity Survey-Adolescent Supplement: Prevalence, Correlates, and Treatment. *Journal of the American Academy of Child & Adolescent Psychiatry*. 54(1):37-44.e32.
4. [name] HK, Lee D, Moore SM. Trust of healthcare provider varies by level of depressive symptoms in adolescents. Society of Adolescent Health & Medicine; March 14, 2018, 2018; Seattle, WA.

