Title: Pilot RCT to Evaluate the Effects of a Trust-Building Depression Management Intervention on Moderate Depressive Symptoms in Low-Income Adolescents

NCT: 03599141

Date IRB approved: 10/13/2022

PROTOCOL TITLE: Study comparing two depression management interventions for teens with depression

PRINCIPAL INVESTIGATOR:

[name], RN
Frances Payne Bolton School of Nursing
[contact]
[contact]

UH FACULTY ADVISOR: N/A

OTHER DEPARTMENTS INVOLVED IN THIS STUDY: Department of Psychology

VERSION NUMBER: 1.16

DATE: 09/28/2022

Study Comparing Two Depression Management Interventions for Teens with Depression

Objectives

(1) Our purpose is to test the Trust-building depression Self-Management Together (**TRUST**) intervention among adolescents with moderate depressive symptoms. Our premise is that trust can be learned, that increasing trust will improve self-regulation, and improved self-regulation will influence depression management behaviors, which will decrease depressive symptoms and increase quality of life (QOL). **The study aims are:**

Aim 1. Compare the effects of the TRUST intervention with a depression management intervention on depression management behaviors (sleep, stress management, medication adherence, appointment keeping) and health status (depressive symptoms, QOL) in adolescents with moderate depressive symptoms.

Aim 2. Assess whether the effects of the TRUST intervention on depression management behaviors (sleep, stress management, medication adherence, appointment keeping) and health status (depressive symptoms, QOL) are mediated by (respiratory sinus arrhythmia [RSA], behavioral interaction assessment, adolescent/parent trust self-reports, relationship quality, self-regulation, family cohesion, social support, decision making, self-efficacy, rumination, decentering).

Aim 3. Assess the effects of potential moderators (gender, race, perceived stress, parental monitoring, household income, parent level of education, parenting style, parent stress) on the relationship between the TRUST intervention and depression management behaviors and health status (depressive symptoms, QOL).

(2) **Hypothesis:** We hypothesize that variations in adolescent/ parent trust-building will predict response to the TRUST intervention and depression management behaviors as evidenced by change in depressive symptoms and QOL.

Background

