(2) Minors will be recruited with permission of the parent/guardian during the process of informed consent with assent designated for acceptance by the minor. Minors are the participant of interest, since this is a pediatric study targeting adolescent participants with depression. The consent/assent document was designed with adolescents in mind, including simple and clear lay language to promote respect for (minor) persons with shared consent/assent decision-making between parent and adolescent. Drs. [name] and [name] have conducted previous research protocols that involve adolescent-parent dyads and have experienced research assistants and established protocols for quality assurance, crisis intervention and referral, as well as initial and ongoing staff training. The research assistants hired for this project will have prior experience working with adolescent-parent dyads.

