b. **Questionnaires:** Survey data will be collected using REDCap on a tablet computer. Measures used in the study are listed in the Table below. Due to restrictions associated with the COVID-19 pandemic, parents and adolescents will be asked to answer questions privately and at approximately the same time point on an electronic device connected to the internet in their homes. If, for example, only one electronic device is able to connect to the internet, the adolescent can complete the survey and then pass the device to the parent for survey completion. We are assessing families for internet access and device availability in the screening form. For families that do not have a device, we will mail them a tablet that they will mail back to us at the end of the study.

Study Variables, Measures, and Data Collection Points						
ADOLESCENT SURVEY						
Variable	Instrument	Title on Survey	B	3M	6M	
Depressive symptoms	Patient Health Questionnaire-8 ¹⁹	Depression Questions	X	X	X	
Quality of life	Youth Quality of Life-Short Form ²¹	Quality of Life Questions	X	X	X	
Sleep	PROMIS sleep disturbance-4 ²⁵ Children's Report of Sleep Patterns ²²	Sleep Questions More Sleep Questions	X X	X X	X X	
Stress management	Adolescent Lifestyle Questionnaire—stress management subscale ²³	How do you handle your stress?	X	X	X	
Medication adherence	Extent of Medication Adherence ²⁴	Medication Questions	X	X	X	
Appointment keeping	Hill-Bone Compliance Scale ²⁵	Appointment Questions	X	X	X	
Biologic Trust	Respiratory sinus arrhythmia ¹³	Not applicable—assessment in lab	X	X		
Behavioral Trust	Behavioral interaction assessment ¹⁴	Not applicable—assessment in lab	X	X		
Cognitive Trust	Children's General Trust Scale ²⁶	Children's Trust Questions	X	X	X	
Cognitive Trust	Parent Trust of Child Scale—Adolescent perceived ²⁷	Parental Trust Questions	X	X	X	
Relationship quality	Inclusion of Other in Self ²⁸	How close are you with your parent?	X	X	X	
Self-regulation	Positive and Negative Affect Schedule ²⁹	Emotion Questions	X	X	X	

Family cohesion	Brief Family Relationship Scale ³⁰	Family Relationship Questions	X	X	X
Rumination	Children's Response Style Questionnaire ³²	How do you handle sadness?	X	X	X
Self-efficacy	PROMIS Self-efficacy - Youth ³¹	Getting stuff done questions	X	X	X
Decentering	Experiences Questionnaire ³³	Self-awareness Questions	X	X	X
Demographics	Demographics questionnaire	Who are you?	X		
Perceived stress	Perceived Stress Scale-Peds ³⁴	Stress Questions	X	X	X

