COVID anxiety	COVID anxiety-5	COVID anxiety	X	X	X
Anxiety symptoms	PROMIS-25 Pediatric ¹⁹	Health Questions	X	X	X
Executive function	Pediatric Cognitive Function Short Form ³⁵	Thinking Questions	X	X	X
Parenting monitoring	Parental Monitoring Scale ³⁶	How much do your parents keep an eye on you?	X	X	X

PARENT SURVEY

Biologic Trust	Respiratory sinus arrhythmia ¹³	Not applicable—assessment in lab	X	X	
Behavioral Trust	Behavioral interaction assessment ¹⁴	Not applicable—assessment in lab	X	X	
Cognitive Trust	Parent Trust of Child Scale—Parent ²⁷	Parent's Trust of Child Questions	X	X	X
Relationship quality	Inclusion of Other in Self ²⁸	How close are you with your teen?	X	X	X
Relationship quality	Parent-Child Coercion Scale ³⁷	Parent-Child Communication Questions	X	X	X
Demographics	Demographic questionnaire	Who are you?	X		
Parenting style	Alabama Parenting Questionnaire-Shor ³⁸	Parenting Style Questions	X	X	X
Parent stress	PROMIS Perceived Stress Scale ³⁴	Stress Questions	X	X	X
General health	PROMIS-25 ¹⁹	General Health Questions	X	X	X

Note. B = baseline, 3M = 3 months, 6M = 6 months

We are also providing families with information about free or reduced cost internet access and free internet hot spots in the community (attached). Once restrictions associated with the COVID-19 pandemic are eased, in-person data collection will resume. Parent and adolescent will simultaneously answer questions on separate computers in a private room. This is intended to allow both to answer questions privately and to prevent parents from interfering with adolescent responses. During social distancing due to novel coronavirus-19, we will email a link to the questionnaire to participants. All materials will be assigned a unique number that will be used to link data over time. A master list linking the ID number to the participant's name will be kept in a password-protected computer file, in a locked office, at the local site. This list will be kept entirely separate from the data so that responses cannot be linked to the individual participant.

c. The risks associated with gathering information from participants by properly trained and supervised research assistants are low. Participants may experience discomfort by

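### Does it matter that two Aim 2 mediators, social support and decision making, have no named instrument?

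*Combined protocol and SAP*

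**What the plan says.** The Objectives state the premise: trust can be learned, more trust improves self-regulation, and better self-regulation improves depression management behaviors and, through them, symptoms and quality of life. Aim 2 then asks whether the effects of TRUST "are mediated by (respiratory sinus arrhythmia [RSA], behavioral interaction assessment, adolescent/parent trust self-reports, relationship quality, self-regulation" and a further six constructs: "family cohesion, social support, decision making, self-efficacy, rumination, decentering".

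Under Study Design, Procedures, and Timeline, item b (Questionnaires), the protocol says: "Measures used in the study are listed in the Table below". The table that follows has an adolescent part and a parent part. Each row gives a variable label, an instrument and the visits (baseline, 3 months, 6 months). No row is labelled social support or decision making.

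The Data Analysis Plan is three sentences of method. It assigns a linear mixed effects model to Aims 1 and 2 and names no mediator. The phrase "we will apply usual mediation techniques" is attached to Aim 3, the moderator aim, so it says nothing about what was meant for these two constructs.

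**The concern.** An aim that names a mediator implies that the mediator is measured. Where the aim and the measures table disagree, a reader suspects one of two things.

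The first is that a scale will be chosen for the construct once the data are in hand. The mediator is then the analyst's choice rather than a planned variable.

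The second is that nothing will be reported. A reader of the results then cannot tell a mediator that was tested and left out from one that was never measured. With eleven mediators and six outcomes in play, that distinction is worth having.

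**Working it through.** There is no sample-size, power or alpha figure to reproduce. The check is a count and a match of Aim 2 against the table.

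**Inputs.** Aim 2 names eleven mediators when the adolescent/parent trust self-reports are counted once, as the aim writes them. The table has 22 adolescent rows and 9 parent rows: 22 + 9 = 31.

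| Aim 2 mediator | Rows in the table | Visits |
|---|---|---|
| RSA | 2 (adolescent, parent) | baseline, 3 months |
| Behavioral interaction | 2 (adolescent, parent) | baseline, 3 months |
| Trust self-reports | 3 (two adolescent, one parent) | all three |
| Relationship quality | 3 (one adolescent, two parent) | all three |
| Self-regulation | 1 | all three |
| Family cohesion | 1 | all three |
| Self-efficacy | 1 | all three |
| Rumination | 1 | all three |
| Decentering | 1 | all three |
| Social support | 0 | none |
| Decision making | 0 | none |

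Mediator rows: 2 + 2 + 3 + 3 + 1 + 1 + 1 + 1 + 1 = 15, covering 9 of 11 mediators (9/11 = 82%). Without a row: 2/11 = 18%. The other 31 − 15 = 16 rows are 6 outcome rows, 6 moderator rows and 4 that belong to no stated aim.

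**Is either construct measured elsewhere?** Social support is mentioned only in Aim 2. Decision making comes up again only under Vulnerable Populations, where it concerns "shared consent/assent decision-making between parent and adolescent". The procedures name no other instrument for either, and no title in the reference list identifies one.

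**Could a row have dropped out of the table?** Probably not. References 21 to 38 are each cited by a row that is present, so none in that run is left over for a lost row. This is support rather than proof, because the citations are not all well matched: reference 31, cited for self-efficacy, is titled as a cognition battery.

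**Could a collected scale have been meant?** Possibly. The executive function row uses the "Pediatric Cognitive Function Short Form", which might stand in for decision making, and one of the family or relationship scales might stand in for social support. The table's labels do not settle it. The Brief Family Relationship Scale is filed under family cohesion, while its cited title speaks of the relationship dimension of family functioning more broadly. Items and subscales are not in the documents, so the evidence supports saying that no instrument is named or mapped. It does not support saying that Aim 2 cannot be carried out for these two constructs.

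**What would an edit change?** There are two possible edits.

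- Map each construct to a scale already in the table. The data collected are the same as before.
- Delete the two constructs from Aim 2. The aim becomes narrower, and again the data are the same.

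Under either edit the Aim 1 comparisons, the Aim 3 moderator analyses and the results for the nine measured mediators stay as they were.

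**The case for a change.** The best argument for acting is that it costs almost nothing: a line in Aim 2, or up to two table entries. An exploratory label does not excuse a trial from saying what it measured. A mapping made late is open to choice. Family cohesion and relationship quality are already separate Aim 2 mediators, so reusing one of those scales for social support would count one scale as two mediators.

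Much of this stands. The count is right, the ambiguity is real, and a proxy picked after the data are seen would be a post hoc analysis.

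What does not stand is that editing these words would much reduce analyst choice. Nine mediators are already served by 15 rows, with three rows each for trust and relationship quality. No mediator is ranked as primary, and the Data Analysis Plan gives no mediator model. Settling two unlabelled constructs leaves nearly all of that latitude in place. The reporting worry also has an ordinary answer: a mediation report names the scale behind each mediator, and a construct with no scale shows as not measured. A reader who has the table can already see which two those are.

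**Conclusion.** The mismatch between Aim 2 and the measures table is genuine and small: 2 of 11 mediators (18%) have no named instrument, or 2 of 12 (17%) if the adolescent and parent trust reports are counted separately. It is a documentation gap in an exploratory aim of a 30-dyad pilot. The constructs that carry the stated premise, trust and self-regulation, each have survey instruments at baseline, 3 months and 6 months. Analysts can be expected to work from the scales that were collected and to say which those were. Mapping or deleting the two constructs would leave the data, the other estimates and the conclusions as they are, so no change is called for.

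This rests on two assumptions: that the table is complete as published, and that any later use of a proxy for either construct would be presented as exploratory. The 82% coverage describes named rows, not data in hand. The RSA and behavioral interaction assessments are stated to be paused under COVID-19 restrictions, which is a separate matter.
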